8.0 TOXICITIES TO BE MONITORED AND DOSAGE MODIFICATIONS

Dose modifications will be performed as outlined in Section 8.0 of the main SELECT protocol (**S0000**).

9.0 STUDY CALENDAR

There are no scheduled study parameters to be followed for this study.

10.0 CRITERIA FOR EVALUATION AND ENDPOINT DEFINITIONS

All medical records obtained from the ophthalmologist/optometrist will be collected and reviewed at the SEE Center. Upon receipt of the medical record release form from the Study Site, the SEE Center will send a letter, a copy of the signed medical record release form, and a questionnaire to the ophthalmologist/optometrist asking about the reported diagnosis. Alternatively, the Study Site may request the medical records from the ophthalmologist/optometrist, collect the detailed questionnaire and forward all materials obtained to the SEE Center.

The AMD questionnaire will ask about (a) the date of initial diagnosis of AMD; (b) the best-corrected visual acuity at the time of diagnosis; (c) the date when visual acuity was first noted to be 20/30 or worse (if different from the date of initial diagnosis); (d) pathological findings observed (drusen, retinal pigment epithelium hypo/hyperpigmentation, geographic atrophy, retinal pigment epithelial detachment, subretinal neovascular membrane, or disciform scar) when AMD was first diagnosed; (e) pathological findings observed when visual acuity was first noted to be 20/30 or worse; (f) the date when exudative (wet) AMD was first noted (defined by presence of retinal pigment epithelium detachment, subretinal neovascular membrane, or disciform scar); (g) whether there are other ocular abnormalities which would explain or contribute to visual loss; (h) whether AMD, by itself, is significant enough to cause the vision to be reduced to 20/30 or worse; (i) whether laser treatment or photodynamic therapy was performed for AMD.

The cataract questionnaire will ask about (a) the date of initial diagnosis of cataract; (b) the best-corrected visual acuity at the time of diagnosis; (c) the date when visual acuity reached 20/30 or worse (if different from the date of initial diagnosis); (d) the date of cataract extraction; (e) whether there were other ocular abnormalities which could explain loss of visual acuity; (f) if other ocular abnormalities, whether cataract, by itself, is significant enough to cause the vision to be reduced to 20/30 or worse; (g) etiology of cataract (including age-related, traumatic, congenital, inflammatory, or surgery or steroid induced); (h) cataract type (nuclear, cortical, posterior subcapsular, other).

Ophthalmologists and optometrists may supply the requested information by providing photocopies of the relevant medical records instead of completing the forms.

Once obtained, the questionnaires and medical records will be reviewed by the Study Coordinator to determine their conformity with uniform diagnostic criteria.

Three categories of the AMD endpoint are defined: (a) AMD - self-report confirmed by medical record evidence of a diagnosis of AMD subsequent to randomization to SELECT (S0000); (b) AMD with vision loss - as in (a) but with vision loss to 20/30 or worse attributable to AMD (visually-significant AMD); (c) advanced AMD - as in (b), but including evidence of geographic atrophy or exudative disease.

The primary AMD endpoint in this eye study, visually-significant AMD, will, on average, represent a less severe stage of disease than cases meeting the criteria for advanced AMD in AREDS. In our other ongoing trials in men and women (Physicians' Health Study, Women's Health Study, Women's Antioxidant Cardiovascular Study) approximately 60 - 65% of cases meeting the criteria of vision loss to 20/30 or worse attributable to AMD are characterized by early signs of AMD only (i.e. some combination of drusen and/or retinal pigment epithelium changes). Thus, the primary AMD endpoint of visually-significant AMD will provide a meaningful test of whether antioxidant vitamins can be effective in lowering risks of earlier stages of AMD. In secondary analyses, we propose to examine whether the study agents reduce the risk of advanced AMD (cases with evidence of geographic atrophy or exudative disease) as well as total AMD including cases with and without vision loss.

Two cataract endpoints are defined: (a) cataract - self-report confirmed by medical record evidence of a diagnosis of age-related cataract subsequent to randomization to SELECT (S0000), with best-corrected visual acuity of 20/30 or worse due to cataract; (b) extraction - surgical removal of an incident cataract.

The primary cataract endpoint in this eye study provides a meaningful test of whether antioxidant vitamins can be effective in lowering risks of visually significant lens opacities. In secondary analyses, we propose to examine whether the study agents reduce the risk of cataract surgery as well as subtypes.

11.0 STATISTICAL CONSIDERATIONS

11.1 Power Estimates:

In this section we have computed the statistical power of the trial to detect plausible effects of vitamin E and selenium on the primary endpoints of visually-significant AMD and cataract among the anticipated 32,400 randomized men. Power is estimated with length of follow-up at planned termination (median follow-up, 8.8 years). Estimates of power are based on a two-sided log-rank test comparing event times between treatment groups at the 0.05 significance level. We use the formulas provided by Lachin and Foulkes with the following assumptions:

- a. For both primary endpoints of visually significant AMD and cataract, we have used the event rates in Physicians' Health Study I to calculate the number of cases expected at the end of the planned length of follow-up of 8.8 years (median).
- b. We assume that the age distribution of all participants in SELECT at randomization will match the age distribution of the randomized participants during the first 5 months of the trial (July-December, 2001). Further, we assume that the percentages of participants within each 5-year age group who have visually significant AMD or cataract at randomization will match the corresponding observed percentages in Physicians' Health Study I.
- c. Applying physician rates to the projected randomized sample in SELECT, we anticipate that at baseline, 30,250 men will be free of a diagnosis of cataract, and 31,580 men will be free of a diagnosis of AMD. Also based on physician rates and the projected age distribution of the SELECT population, we assume that the rate of visually-significant AMD in the placebo group will be 3 events per 1,000 person-years, and the rate of cataract in the placebo group will be 10 events per 1,000 person-years.
- d. Study duration will be 10 years with a minimum of 7 years of treatment.
- e. Based on experience with similar trials, we expect the combined loss to follow-up, from both death and drop-out, to be less than 5 per 100 person-years. This rate is used in power calculations.

For the primary endpoint of visually-significant AMD, the study will have good power (80% or greater) to detect an observed RR 0.80 at the end of the total planned follow-up (median, 8.8 years). For the primary endpoint of cataract, the study will have excellent power (90% or greater) to detect an observed RR as low as 0.85 at the end of the total planned follow-up.

Power (%) for the main effects of vitamin E and selenium on the primary endpoints of visually-significant AMD and cataract with total planned follow-up.

		Total Planned Follow-Up (8.8 Years Follow-Up)	
Observed RR	True RR (assuming 100% compliance)	Visually-significant AMD	Cataract
0.85	0.79	54.4	92.0
0.80	0.72	79.9	99.6
0.75	0.66	94.4	> 99.9
0.70	0.59	99.1	> 99.9
0.65	0.52	99.9	> 99.9

11.2 Secondary Comparisons:

Concerning the secondary endpoint of advanced AMD, with total planned follow-up we expect to have good power (80% or greater) to detect a benefit of treatment of 30% or greater. For the secondary endpoints of total AMD (with or without vision loss) and cataract surgery, we expect to have excellent power (90% or greater) to detect a benefit of treatment as small as 20% at the end of total planned follow-up.

11.3 Data Analysis Plan:

The study design is a 2 x 2 factorial trial of selenium (200 µg daily) and vitamin E (400 mg daily). Because of the large sample size, randomization should virtually assure that both known and unknown confounding variables will be distributed evenly among the treatment groups. Any imbalances that may occur with respect to known risk factors for AMD and cataract, or any medical or ocular condition which would require more medical attention thus increasing the likelihood of a diagnosis of AMD or cataract, will be controlled for in subsequent analyses.

Primary analyses will examine the main treatment effects of each study agent, and thus will differ from the primary analyses in the main SELECT study. Analyses of the main treatment effects will be based on the intent-to-treat principle with participants classified according to their randomized treatment assignment. Initial analyses of the AMD and cataract endpoints will include simple contingency tables in which the rate of each endpoint in terms of number of events per person-year of observation among participants allocated to active treatment will be compared with the incidence among those allocated to its placebo. For example, the incidence rate of AMD over the period of follow-up among participants assigned to active vitamin E will be compared with the rate for participants assigned to vitamin E placebo, controlling by stratification for selenium assignment. Similar analyses will separately examine the effects of selenium on the incidence of AMD, as well as the effects of vitamin E and selenium on the incidence of cataract. In addition, Kaplan-Meier survival estimates, the logrank test, and proportional hazards regression models will be used to determine whether there is a difference in time to diagnosis of AMD or cataract. (25 - 27) We will test for possible interaction of study agents by including an interaction term in proportional hazards regression models. Because an extended exposure to the study agents may be required to observe an effect, analyses will also be conducted which exclude AMD or cataract that develop during

the early years after randomization. Proportional hazards regression models will be used to evaluate smoking as a modifier of effects on AMD and cataract, and to evaluate effect modification by other factors including baseline dietary levels of the study agents. Additional analyses will separately evaluate the effect of vitamin E and selenium on the incidence of cataract surgery and cataract subtypes, and the incidence of advanced AMD (geographic atrophy and exudative AMD) and total AMD (with or without vision loss).

The primary analyses will consider individuals, rather than eyes, as units of analyses. This is consistent with current practice for survival analysis of ophthalmic trials when the individual, rather than the eye, is the unit of randomization. Some increase in statistical power would likely be obtained by considering eyes as the units of observation. Rosner has described an approach for estimation of parameters in logistic regression models that accounts for the correlation in disease risk between fellow eyes. (28) We will apply this model of Rosner to estimate the cumulative risk of developing an outcome in one eye given the treatment status of the individual and accounting for other baseline predictors. An additional benefit of this approach is that it explicitly quantifies the odds of an outcome in an eye given the outcome status of the fellow eye.

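### Section 11.3 ties covariate adjustment to observed imbalance and leaves age at randomization out of the main model; a fixed age-adjusted primary Cox model would be a small, free improvement

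*Combined protocol and SAP*

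**What the plan says.** Section 11.3 (Data Analysis Plan) first argues that the large sample should make randomization balance the confounders. It then says that two things will be controlled for in later analyses: "Any imbalances that may occur with respect to known risk factors for AMD and cataract", and imbalances in "any medical or ocular condition which would require more medical attention thus increasing the likelihood of a diagnosis" of either disease. It lists no covariates and does not say how large an imbalance must be to count.

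The main-effect analyses that follow are intent-to-treat. Event rates per person-year are compared between an agent and its placebo, stratified by the other agent. In addition, "Kaplan-Meier survival estimates, the logrank test, and proportional hazards regression models will be used" to look for a difference in time to diagnosis. None of these is named as the decisive test, and the covariates of the regression model are not given.

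Section 11.1 (Power Estimates) is clearer on the test: "Estimates of power are based on a two-sided log-rank test comparing event times between treatment groups at the 0.05 significance level". It also treats age as a determinant of both diseases. Baseline prevalence is projected by 5-year age group, and the placebo event rates are derived from the projected age distribution. Age at randomization is therefore already recorded.

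**The concern.** Three features sit badly together. Adjustment depends on what the data show. The result that counts is not identified among several. The one covariate that the sponsor's own projections rely on has no fixed place in the model.

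Two things could be at stake. When risk varies with age, a comparison that ignores age estimates a hazard ratio slightly closer to 1 than the age-specific one, and so gives up some power. And where unadjusted and adjusted results are both available with neither named as primary, a reader cannot verify that the reported one was fixed in advance. This applies to four primary hypotheses: two agents on two endpoints (Section 1.1).

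**Working it through.** **Inputs from Section 11.1.** Two-sided log-rank test at 0.05. For cataract, "we anticipate that at baseline, 30,250 men will be free of a diagnosis of cataract" and "the rate of cataract in the placebo group will be 10 events per 1,000 person-years". For AMD, "31,580 men will be free of a diagnosis of AMD" and "the rate of visually-significant AMD in the placebo group will be 3 events per 1,000 person-years". Duration is 10 years with a minimum of 7, taken here as uniform entry over 3 years. Loss is 5 per 100 person-years. Equal allocation at the margins of the factorial is assumed.

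**Step 1: the plan's own figure.** For cataract at RR 0.85 these inputs give about 1,864 events (about 6% of 30,250 men). The Schoenfeld formula is

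power = Φ(|ln RR| × √(D/4) − 1.96) = Φ(0.1625 × √(1,864/4) − 1.96) = Φ(1.55) = 93.9%.

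The Lachin-Foulkes formula gives 93.8%. The plan states 92.0%, which is within 2 points. At RR 0.80 Lachin-Foulkes gives 99.7% against 99.6% stated. For AMD at RR 0.80 the same inputs give 76.5% against 79.9% stated, so AMD is used below only for the difference between the two models.

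**Step 2: what age adjustment adds.** The documents give neither the age effect nor the age distribution. Assumed: age normal with mean 63 and SD 6 to 8, truncated to 55–85, and an age hazard ratio of 1.5 to 4 per decade. For a treatment hazard ratio of 0.85 at a given age, numerical integration over age gives the hazard ratio m that an unadjusted analysis estimates. With k = ln 0.85 / ln m, the gain in effective events is k² − 1. Anchored at the stated 92.0%, adjusted power is Φ((1.405 + 1.960) × k − 1.960).

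| Age HR per decade | m (SD 6; SD 8) | Extra effective events | Adjusted power, from 92.0% |
|---|---|---|---|
| 1.5 | 0.8502; 0.8504 | 0.3%; 0.6% | 92.07%; 92.14% |
| 2 | 0.8507; 0.8512 | 1.0%; 1.8% | 92.25%; 92.43% |
| 3 | 0.8521; 0.8533 | 3.1%; 4.9% | 92.74%; 93.15% |
| 4 | 0.8537; 0.8558 | 5.6%; 8.9% | 93.29%; 93.97% |

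Last entry: k = 0.16252/0.15572 = 1.0437, k² − 1 = 8.9%, and Φ(3.365 × 1.0437 − 1.960) = Φ(1.552) = 93.97%.

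For AMD at RR 0.80, m runs from 0.8001 (age HR 1.5, SD 6) to 0.8024 (age HR 4, SD 8). That is 0.1% to 2.7% more effective events. Unadjusted against adjusted power is 76.8% against 76.8% at the weak end and 75.2% against 76.3% at the strong end.

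**Step 3: simulation check, cataract, RR 0.85.** With 2,500 trials per setting, unadjusted against age-adjusted power was 92.5% against 92.8% (age HR 2), 94.0% against 94.4% (age HR 3) and 91.0% against 93.1% (age HR 4). The Monte Carlo standard error is about 0.5 point.

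**Step 4: type I error under two different rules.** There were 4,000 null trials per setting, with a standard error of √(0.05 × 0.95/4,000) = 0.34 point.

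- Adjust for age only when its imbalance has p < 0.05: 3.9 to 4.9%.
- Report whichever of the unadjusted and adjusted results is more favourable: 5.4 to 5.7%.

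A bivariate normal approximation with correlations of 0.980 and 0.958 between the two test statistics gives 4.9% and 4.8% for the first rule, and 5.9% and 6.3% for the second. The correlation of 0.958 corresponds to the steepest age effect in the table (1/1.0437). The first rule does not inflate error because it is driven by imbalance and not by the outcome: where imbalance is large, the unadjusted statistic is replaced by a correctly centred one.

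**The case against.** The strongest reply is that the plan is valid as it stands. A log-rank comparison that follows the randomization needs no covariates, is the test on which power was computed, and loses little when about 6% of men have an event. Cataract power is already stated as 92.0% at RR 0.85. All of this stands. It means the fix is an improvement in efficiency and clarity and does not correct an invalid test.

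A reader might draw four stronger inferences, which the documents do not support.

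- *That the reported result is a data-driven choice.* Section 11.3 places imbalance control in later analyses and describes a main comparison stratified by the other agent whatever the balance. The natural reading is an unadjusted main result with adjusted follow-up. What remains is that no decisive test is named.
- *That the imbalance trigger inflates type I error.* Step 4 shows that it does not. The inflation belongs to picking the better of two results, a rule the plan nowhere states.
- *That conditions arising after randomization would be adjusted for.* The sentence on imbalances directly follows the one on balance through randomization, so it concerns departures from balance at that point. The clause on conditions needing more medical attention is not expressly limited to baseline, so the other reading is possible, but no passage proposes it.
- *That substantial power is lost.* Step 2 shows about 2 points at most for cataract over the assumed range, and about 1 for AMD.

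**Conclusion.** The point holds as a free improvement. Section 11.3 makes covariate control conditional on an imbalance that it does not define, leaves the decisive test unnamed, and omits age from the main model although Section 11.1 relies on age to project both diseases.

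The size is modest: 0.3 to 9% more effective events for cataract (about 0.1 to 2 power points at RR 0.85) and 0.1 to 3% for AMD (about 1 point at most). These figures depend on an assumed age hazard ratio of 1.5 to 4 per decade and an assumed age distribution. A weaker age effect would make the gain negligible. A free choice between models would raise the 5% error rate to about 5.4 to 6%, slightly more at the steepest age effect considered. That measures what prespecification rules out; it is not an error rate of the plan as written.

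**What to change.** In Section 11.3:

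1. Name one primary test for each agent and each primary endpoint: the treatment term in a Cox model adjusted for age at randomization and stratified by the other agent, two-sided at 0.05, whatever balance is observed. State how age enters (continuous, or in 5-year groups).
2. Describe the rate tables, Kaplan-Meier curves and log-rank test as supportive.
3. Limit any further adjustment to listed variables measured at or before randomization, as sensitivity analyses. This also closes the open reading of the clause on medical attention.
4. Delete the imbalance trigger.

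The cost is SAP wording only, settled before outcomes are compared by arm. Age at randomization and treatment assignment are already collected, and sample size, visits and data collection do not change. The log-rank power statement in Section 11.1 can stay as a slightly conservative basis.

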12.0 DISCIPLINE REVIEW

Discipline review is not applicable to **S0000B** (SEE).

13.0 REGISTRATION GUIDELINES

Registration procedures are specified in the SELECT Study Manual.

14.0 DATA SUBMISSION SCHEDULE

Detailed data completion and submission procedures and schedule are found in the SELECT Study Manual.

15.0 SPECIAL INSTRUCTIONS

Special instructions are included in Section 15.0 of the main SELECT protocol (**S0000**).

16.0 ETHICAL AND REGULATORY CONSIDERATIONS

The following must be observed to comply with Food and Drug Administration regulations for the conduct and monitoring of clinical investigations; they also represent sound research practice:

Informed Consent

The principles of informed consent are described by Federal Regulatory Guidelines (Federal Register Vol. 46, No. 17, January 27, 1981, part 50) and the Office for Protection from Research Risks Reports: Protection of Human Subjects (Code of Federal Regulations 45 CFR 46). They must be followed to comply with FDA regulations for the conduct and monitoring of clinical investigations.

Institutional Review

This study must be approved by an appropriate institutional review committee as defined by Federal Regulatory Guidelines (Ref. Federal Register Vol. 46, No. 17, January 27, 1981, part 56) and the Office for Protection from Research Risks Reports: Protection of Human Subjects (Code of Federal Regulations 45 CFR 46).

Drug Accountability

For each investigational drug supplied for a study, drug disposition (drug receipt, dispensing, transfer or return) shall be maintained on the NCI Investigational Drug Accountability Record. Drug supplies must be kept in a secure, limited access storage area under the recommended storage conditions. During the course of the study, the following information must be noted on the Drug Accountability Record; the ID # and initials of the subject to whom drug is dispensed, the date(s) and quantity of drug dispensed to the subject, and the date(s) and quantity of drug returned to the NCI or transferred to another NCI-approved protocol. These Drug Accountability Records must be readily available for inspection and are open to FDA or NCI inspection at any time.

Adverse Experiences

Any adverse experience, if deemed drug related, must be reported to the Operations Office Adverse Drug Reaction (ADR) representative ([name]) as outlined in the SELECT protocol.

CLOSED/EFFECTIVE 07/15/2015

18.0 MASTER FORMS SET

NOTE: All forms to be utilized for this study will be available via the SELECT Workbench at <http://swog.org>. Forms completion and submission guidelines are found in the SELECT Study Manual.

A copy of the Initial Model Informed Consent document for **S0000B** (SEE) is enclosed and must be reviewed and approved by the institutional IRB before placing a participant on study.
